6.2. Adjustments for Covariates

No statistical inference based on hypothesis testing is planned. Thus, there is no need to adjust for covariates.

6.3. Handling of Dropouts or Missing Data

Intercurrent events (ICH E9[R1]) are events which occur after the treatment initiation and preclude observation of a variable or affect how it should be interpreted. Examples of such events include treatment discontinuation due to death or adverse events (AEs) and loss to follow-up. This section describes 3 missing data imputation methods for handling intercurrent events. Part A utilizes modified nonresponder imputation (mNRI) and nonresponder imputation (NRI) for categorical variables and LOCF for continuous variables. As-observed analysis is used in Part B, thus the patient analysis in Part B will be based on completer of analysis visit only; no missing data imputation method will be applied for Part B.

6.3.1. Modified Nonresponder Imputation (mNRI)

An mNRI method can be justified based on the composite strategy (ICH E9[R1]) for handling intercurrent events. In a composite strategy with NRI, a patient is defined as a responder only if

- (i) they meet the clinical requirements for response at the predefined time, and
- (ii) they remain on the assigned study treatment;

failing either criteria by definition makes them a nonresponder.

For Study JAHW, this definition is modified such that, if either one of (i) or (ii) criteria fails, the patient data will be reviewed by the Clinical Endpoints Committee (CEC) for further responder evaluation.

The primary efficacy outcome variable, that is, the proportion of responders at Week 24 where response is defined according to the SUN criteria as a 2-step decrease in the level of inflammation (anterior chamber cells) or decrease to zero in the eye most severely affected at baseline, will be imputed using mNRI. Patients will be considered a nonresponder for the mNRI analysis if they do not meet the clinical response criteria or are entirely missing the visit at the analysis time due to lack of efficacy. If the primary efficacy outcome variable data are missing for reasons other than this, available preceding data from patients with missing data will be reviewed by an independent and external CEC, as outlined in the CEC charter. The CEC will ensure that patients with missing data are evaluated in a consistent manner. The CEC will consider the complete patient history and the reasons for the missing data, in order to determine whether responder or nonresponder status is appropriate on a case-by-case basis. Study sites should send any requested source documentation to the CEC in a timely fashion.

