10.3. Statistical Analyses

10.3.1. General Statistical Considerations

Statistical analysis of this study will be the responsibility of Lilly or its designee. A detailed SAP describing the statistical methodologies will be developed by Lilly or its designee.

Bayesian analysis will be used as the primary analysis method for the primary endpoint and interim analysis. The posterior probability will be reported and the conclusion will be made based on the prespecified success criteria. The primary endpoint is the proportion of patients with response at Week 24. Response is defined as a 2-step decrease in the level of inflammation (anterior chamber cells) or decrease to zero in the eye most severely affected at baseline, measured by SUN criteria (Jabs et al. 2005). If the study is not stopped for futility, the posterior probability of the treatment response rate exceeding 57% will be calculated, and the study objective will be successfully met (i.e., a positive study) if this probability is at least 80%. The detail of the analyses will be described in the SAP.

Unless otherwise specified, for the endpoints that may relate to both eyes, such as patients with uveitis affecting both eyes, the summary of the data for a given endpoint measure will be based on both affected eyes. The summary statistics may be grouped into “less severely affected eye” and “more severely affected eye,” or “right eye” and “left eye” subgroups. The details will be documented in the SAP.

Efficacy and health outcome endpoints will also be summarized using descriptive statistics for the baricitinib arm and adalimumab arm. No treatment comparison will be conducted.

Continuous data will be summarized in terms of the mean, standard deviation, minimum, maximum, and median. Categorical data will be summarized as frequency counts and percentages.

All safety data will be descriptively summarized.

Any change to the data analysis methods described in the protocol will require an amendment ONLY if it changes a principal feature of the protocol. Any other change to the data analysis methods described in the protocol, and the justification for making the change, will be described in the clinical study report. Additional exploratory analyses of the data will be conducted as deemed appropriate. Complete details of the planned analyses will be documented in the SAP.

The SAP will be approved before the first patient visit in Study JAHW.

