4.1. Primary Objective

The primary objective of Study JAHW is shown in [Table JAHW.4.1](#).

Table JAHW.4.1. Primary Objective and Endpoint

Objectives	Endpoints
To evaluate the efficacy of baricitinib in children with JIA-U or ANA-positive uveitis	Proportion of responders at Week 24. Response is defined according to the SUN criteria as a 2-step decrease in the level of inflammation (anterior chamber cells) or decrease to 0 through Week 24, in the eye most severely affected at baseline.

Abbreviations: JIA-U = juvenile idiopathic arthritis-associated uveitis; SUN = Standardization of Uveitis Nomenclature; ANA = antinuclear antibody.

In compliance with the International Conference on Harmonisation (ICH) E9(R1) guidelines, a study should be clear in defining an estimand framework, which includes 4 attributes:

- the population of interest: the patients targeted by the scientific question;
- the variable (or endpoint) of evaluation that is obtained for each patient, that is required to address the scientific question;
- the population-level summary of the variable, a basis for treatment evaluation; and
- the specification of how to account for intercurrent events to reflect the scientific question of interest.

In particular, for Study JAHW, the primary estimand is defined by

Population of interest: the population of interest for Part A of Study JAHW is patients who participate in Study JAHW Part A. Study JAHW patients are patients from 2 years to <18 years old with active juvenile idiopathic arthritis-associated uveitis (JIA-U), or chronic anterior antinuclear antibody (ANA)-positive uveitis. Analysis populations are defined in [Section 6.1.1](#).

Variable (or endpoint) of evaluation: the primary endpoint/variable is listed in [Table JAHW.4.1](#).

Population-level summary: the primary quantity of interest will be the proportion of responders on baricitinib. Details are given in [Section 6.7](#).

Intercurrent event(s) strategy: in Study JAHW Part A, the analysis population will be based on patients who have had, or would have, the chance to complete the visits. In the estimand framework for binary variables, the composite estimand strategy will be applied and modified non-responder imputation will be used for the primary outcome variable (that is, the proportion of responders at Week 24, where response is defined according to the Standardization of Uveitis Nomenclature [SUN] criteria as a 2-step decrease in the

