7.1. Primary Outcome and Methodology

The primary efficacy endpoint is the proportion of responders at Week 24. Response is defined according to the SUN criteria as a 2-step decrease in the level of inflammation (anterior chamber cells) or decrease to zero in the eye most severely affected at baseline.

A Bayesian posterior probability will be calculated based on the number of observed responders who complete or have the opportunity to complete 24 weeks of Study JAHW at each stage:

- Stage 1: 10 baricitinib-treated patients.
- Stage 2: 20 baricitinib-treated patients.
- Stage 3: up to 30 baricitinib-treated patients.

The details of the calculation of the posterior probability are as follows:

$$X_i: i \text{ th patient}$$

$$X_i | \theta \sim Bern(\theta)$$

$$\theta \sim Beta(1,1)$$

Then,

$$Y^{stage1} = \sum_{i=1}^{10} X_i$$

$$Y^{stage2} = \sum_{i=1}^{20} X_i$$

$$Y^{stage3} = \sum_{I=1}^{30} X_i$$

The Bayesian posterior probability for futility at interim 1 (Stage 1) is calculated as

$$pr(\theta < \text{CCI} | Y^{stage1}) = \frac{\Pr(Y^{stage1} | \theta < \text{CCI}) \cdot \Pr(\theta < \text{CCI})}{\Pr(Y^{stage1})}$$

The Bayesian posterior probability for futility at interim 2 (Stage 2) is calculated as

$$pr(\theta < \text{CCI} | Y^{stage2}) = \frac{\Pr(Y^{stage2} | \theta < \text{CCI}) \cdot \Pr(\theta < \text{CCI})}{\Pr(Y^{stage2})}$$

The Bayesian posterior probability for study success at the end of study (Stage 3) is calculated as

$$pr(\theta > \text{CCI} | Y^{stage3}) = \frac{\Pr(Y^{stage3} | \theta > \text{CCI}) \cdot \Pr(\theta > \text{CCI})}{\Pr(Y^{stage3})}$$

Table JAHW.7.1. Description and Derivation of Secondary Efficacy Outcomes for Part A

Measure	Description	Variable	Derivation / Comment	Definition of Missing

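### SAP 6.3.1 contradicts itself on whether an observed Week 24 nonresponder goes to the Clinical Endpoints Committee (CEC), and leaves the off-treatment observed responder to the CEC despite a stated composite strategy

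*SAP*

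**What the plan says.** SAP 6.3.1 starts from the usual composite rule with two conditions: (i) clinical response at the predefined time and (ii) still on the assigned treatment. Under that rule, "failing either criteria by definition makes them a nonresponder". It then changes the rule for this study: "if either one of (i) or (ii) criteria fails, the patient data will be reviewed by the Clinical Endpoints Committee (CEC"). The patient's data are to be "reviewed by the Clinical Endpoints Committee (CEC) for further responder evaluation". The sentence is not limited to missing data.

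The following paragraph gives the working rule: "Patients will be considered a nonresponder for the mNRI analysis if they do not meet the clinical response criteria". A visit missed because of lack of efficacy is treated the same way. CEC review is then described only for primary data missing for other reasons, under a CEC charter that is not among the documents.

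Protocol 10.3.1 gives the CEC the same limited scope. Its modified nonresponder imputation (mNRI) text covers missing data only and does not mention observed failures or patients who stopped treatment. SAP 6.3.1.1 applies plain nonresponder imputation (NRI) to the other binary endpoints and excludes the primary. SAP 4.1 states that "the composite estimand strategy will be applied and modified non-responder imputation will be used for the primary outcome variable".

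**The concern.** Two kinds of patient with an observed Week 24 examination are affected.

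- **Examined, no response.** The modifying sentence refers this patient to the CEC. The next paragraph makes the patient a nonresponder with no referral. No text says which sentence governs.
- **Examined, response, but off assigned treatment.** Protocol 5.1.4 allows patients to stay in the study after stopping drug, so this can happen. The patient fails only (ii). The working paragraph does not reach the case, because the response criteria are met and nothing is missing. Only the modifying sentence applies, and the considerations listed for the CEC concern missing data. A composite strategy would point to nonresponder.

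The study's conclusion is a single responder count from an open-label arm, set against a fixed posterior cut-off. Who may be reclassified, and by whom, should be settled before the count is made.

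**Working it through.** **1. The rules side by side**

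| Patient at Week 24 | SAP 6.3.1, modifying sentence | SAP 6.3.1, next paragraph | Protocol 10.3.1, mNRI text |
|---|---|---|---|
| Observed, no response | CEC review | Nonresponder | Not stated; nonresponder is implied by the response definition and the CEC's scope |
| Observed response, off treatment | CEC review | Not addressed | Not addressed |
| Missing, lack of efficacy | CEC review | Nonresponder | Nonresponder |
| Missing, other reason | CEC review | CEC review | CEC review |

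The columns agree fully only in the last row. The protocol's implied entry in the first row rests on its definition: "Response is defined as a 2-step decrease in the level of inflammation (anterior chamber cells) or decrease to zero".

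**2. Inputs for the sensitivity check**

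- Prior Beta(1,1): Protocol 10.3.3.1 and SAP 7.1.
- Success if Pr(θ > 0.57) is at least 0.80: Protocol 10.3.1.
- Futility stop if Pr(θ < 0.40) exceeds 0.75, at 10 and at 20 patients: Protocol 10.3.7 and SAP 10.1.
- Baricitinib patients: at least 20 evaluable (Protocol 10.1), up to 30 at Stage 3 (Protocol 10.3.3.1).

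With y responders among n, θ | y ~ Beta(1 + y, 1 + n − y). Write F for its distribution function. Then Pr(θ > 0.57) = 1 − F(0.57) and Pr(θ < 0.40) = F(0.40).

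**3. The plan's own figures, reproduced**

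- Success at 20/30, Beta(21, 11): 1 − F(0.57) = 0.848, above 0.80 as Protocol 10.1 states.
- Futility at n = 10: 2 responders, Beta(3, 9), gives F(0.40) = 0.881 (stop); 3 responders, Beta(4, 8), gives 0.704 (continue).
- Futility at n = 20: 6 responders, Beta(7, 15), gives 0.7998 (stop); 7 responders, Beta(8, 14), gives 0.651 (continue).

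These match the stated stopping boundaries of 2 or fewer of 10 and 6 or fewer of 20.

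**4. Effect of one classification on the final verdict**

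| n | One short: y | Posterior | Success: y | Posterior |
|---|---|---|---|---|
| 20 | 13 | 0.7476 | 14 | 0.8684 |
| 21 | 14 | 0.7995 | 15 | 0.9005 |
| 22 | 14 | 0.7181 | 15 | 0.8429 |
| 23 | 15 | 0.7718 | 16 | 0.8785 |
| 24 | 15 | 0.6902 | 16 | 0.8177 |
| 25 | 16 | 0.7450 | 17 | 0.8562 |
| 26 | 17 | 0.7928 | 18 | 0.8878 |
| 27 | 17 | 0.7193 | 18 | 0.8337 |
| 28 | 18 | 0.7684 | 19 | 0.8680 |
| 29 | 18 | 0.6945 | 19 | 0.8112 |
| 30 | 19 | 0.7447 | 20 | 0.8478 |

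At each n, the two rows of counts differ by one patient and fall on opposite sides of 0.80. No reclassification rate is assumed.

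**The case against.** The strongest reply is that the context already limits the CEC to missing data. Section 6.3 is about dropouts and missing data and says: "This section describes 3 missing data imputation methods for handling intercurrent events". The only text that lets the CEC decide status concerns missing data. Protocol 10.3.1 agrees, and SAP 7.1 says: "A Bayesian posterior probability will be calculated based on the number of observed responders". The modifying sentence also prescribes a review and not a result, so an observed nonresponder might be reviewed and still be counted as a nonresponder. I accept that the narrow reading is clearly the better one. It does not remove the conflict: the broad sentence is the one that says what is modified in this study, and a review for responder evaluation has no purpose if the answer is already fixed.

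It can also be said that the off-treatment observed responder does have a disposition, namely CEC review, and that the criteria may be in the charter. That is fair. What remains is that the SAP shows no criterion and does not reconcile this route with Section 4.1.

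Finally, one patient changes the verdict at the threshold in any small binary endpoint. That is correct, and the table in the working measures sensitivity only.

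A reader might go further and infer that the plan means the CEC to turn observed failures into responses, or that the response rate will be inflated. The documents do not support this. No sentence gives the CEC that power explicitly, the committee is independent and external, and its review of missing data is openly prespecified.

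**Conclusion.** The contradiction within SAP 6.3.1 is real and should be fixed. One rule opens an observed nonresponse in an open-label arm to case-by-case review; the other, supported by the protocol's CEC scope, closes it. The off-treatment observed responder is a related but lesser point: the route is stated, but it is not aligned with the composite strategy.

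The size can be given only as sensitivity. For every final n from 20 to 30, the posterior one responder short of success lies between 0.690 and 0.7995, and at the success count between 0.811 and 0.901. This rests on the Beta(1,1) prior and on the 57% and 80% thresholds in the protocol. How many patients would fall into either category, and what the CEC would decide, cannot be known from the documents. The charter may settle part of this, but the SAP should not depend on that.

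**What to change.** Replace the modifying sentence in SAP 6.3.1 with wording to this effect:

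> In this study the rule above is changed in one respect only: where Week 24 primary efficacy data are missing and the reason is not lack of efficacy, the CEC determines responder status. A patient whose observed Week 24 assessment does not meet the response criteria is a nonresponder and is not referred to the CEC. A patient with an observed Week 24 response who is no longer on assigned treatment is a nonresponder under the composite strategy in Section 4.1.

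Simply deleting the sentence would not do. The unmodified composite rule would then sit directly before CEC review of missing data, and the off-treatment responder would change status without any statement.

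The last sentence of the replacement is a choice about the estimand. Under it, a patient who stopped treatment and has missing data can still be assigned responder status, while one with an observed response off treatment cannot. If the sponsor prefers CEC review for the latter, the SAP should say so, and Section 4.1 should be aligned.

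Also report how many responders the CEC assigned, and the posterior probability under plain NRI as a sensitivity analysis. The SAP lists no such run for the primary endpoint.

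The cost is an SAP wording change and one further run of the same calculation. The CEC scope would match Protocol 10.3.1, so the limitation to missing data needs no protocol change. The downside is that a possibly lower figure will stand beside the primary result.

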6.3.1.1. Nonresponder Imputation (NRI)

An NRI imputation method can be justified based on the composite strategy (ICH E9R1) for handling intercurrent events. In a composite strategy with NRI, a patient is defined as a responder only if

- (i) they meet the clinical requirements for response at the predefined time, and
- (ii) they remain on the assigned study treatment;

failing either criteria by definition (i) or (ii) makes them a nonresponder.

Binary efficacy and health-outcome variables, excluding the primary outcome variable, will be imputed using NRI. Patients will be considered a nonresponder for the NRI analysis if they do not meet the clinical response criteria or are entirely missing the visit at the analysis time point. Patients without at least 1 postbaseline observation will also be defined as nonresponders for the NRI analysis.

6.3.2. Last Observation Carried Forward (LOCF)

According to ICH E9(R1), the while-on-treatment strategy could be applied based on the last postbaseline value at or before the visit of interest while the patient was still on the study drug.

All continuous endpoints will be imputed using the LOCF methodology after censoring those who discontinued the study drug. For patients who permanently discontinue study treatment or discontinue from Study JAHW for any reason at any time, the last nonmissing postbaseline observation on or prior to discontinuation will be carried forward to subsequent time points for evaluation.

6.3.3. As-observed Analysis

For Part B of Study JAHW, the population of interest is formed by patients who complete through the analysis time as assigned. Thus, the as-observed analysis will be used for Part B. Therefore, this estimand is conditional and targets the effect of treatment conditional on completion of treatment through the time point of interest.

Only data observed at the time of interest are relevant and included in the analyses. There is no need to deal with missing data, as the population consists only of patients with observed data.

